## Research Design and Methods

The proposed study is a pilot RCT with multi-method longitudinal assessment (refer to **Figure 1** for an overview of study activities). The study has three primary aims: (1) to assess the feasibility of recruiting Veterans of color into an RCT of RBSTE, (2) to understand Veterans' views of the acceptability and appropriateness of intervention content and provider behavior and the feasibility of participation in a future RCT; and (3) to refine a holistic assessment strategy.

**Figure 1.** Schematic of study activities

Veterans who express interest in study participation will be contacted by study staff and provided with general information about the study. Those who continue to be interested will engage in the informed consent process in person or using remote procedures (e.g., VA Docusign), depending on personal and health considerations. Veterans who provide written consent will go on to complete the baseline assessment (refer to **Assessment approach**). Randomization will occur at the group level: once a cohort of 4-10 Veterans has enrolled and completed the baseline assessment, the cohort will be randomized by the study statistician. Although group randomization has disadvantages as compared to individual randomization (e.g., dependence among group members, lack of blinding of the final 1-2 groups), these can be managed and are outweighed in our experience by facilitating recruitment because groups can begin more quickly. Groups will meet in **weekly 90-minute sessions for 8 weeks**. Videoconferencing will be used to minimize barriers to participation, including transportation and public health concerns. The assessment battery will be repeated at the end of the group. Participants will be compensated \$50 for each assessment point for total compensation of \$100.

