**Participants.** Veterans ( $n \approx 48$ , potential range 24-60) will be recruited from medical (e.g., primary care) and mental health programs throughout the facility and from the community. Given the feasibility aim of this project, ability to participate is intentionally broad to demonstrate demand and maintain ecological validity. Thus, inclusionary criteria are as follows: (1) self-identified as a BIPOC, (2) Veteran, (3) age 18 or older, (4) able to consent to study activities, and (5) endorsing one or more perceived discrimination experiences on the *Everyday Discrimination Form* (short version) or the *Major Experiences of Discrimination Scale* (abbreviated version; Sternthal, Slopen & Williams, 2011) "a few times a year" or more frequently and endorsing stress on a validated single-item measure (Elo, Leppanen, & Jahkola, 2003). Exclusionary criteria include: (1) serious mental illness, alcohol/substance use disorders, or cognitive impairment that may interfere with the ability to benefit from group (e.g., severe depression, psychotic illness, mania, dementia, **untreated** alcohol/substance dependence); and (2) serious suicidality or homicidality (e.g., ideation with plan/intent) that is likely to require urgent/emergent intervention within the study period.

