**Interventions.** Therapists in both conditions will be VA mental health providers with training in culturally sensitive care **via attending a webinar provided by the Cohen Veterans Network**. [name] will be **responsible for training and providing regular supervision to RBSTE therapists, and they will attend a monthly national consultation call with subject matter experts. Fidelity will be monitored by Drs. [name] and [name] using standard fidelity forms, adapted from [name] previous trial involving PCT (Lang et al., 2017)**. The experimental condition is **RBSTE** (refer to **Appendix 14 for the RBSTE manual**). **RBSTE** begins with "Conocimiento," an introductory exercise focused on normalizing Veterans' experiences with race and reflecting on how their identity formation has been affected by both positive and negative experiences with race. Each session includes psychoeducation about various forms of racism and its adverse mental and physical effects, based on Carter's (2007) race-based traumatic stress model. This process also creates a shared language for communicating about these concerns and for self-advocacy. The concept of advocacy is then used to build resilience and combat messages and experiences of hopelessness and helplessness. Cultural sharing is incorporated weekly to engender pride in one's racial/ethnic identity, combat negative messages regarding racial/ethnic identity, and promote positive and empowering cultural identification. A weekly Empowerment Process Journal is assigned to aid in buffering the oppressive effects of racial trauma and discrimination.

**PCT** is a manualized, supportive, present-focused psychotherapy. **[name] will provide training and ongoing supervision in PCT, and [name] will monitor fidelity.** Therapists focus on current

challenges in participants' lives. Therapists do not teach specific skills but rather draw on the wisdom and experience of group members to address stressors. Common therapeutic techniques include mirroring participants' experiences and non-directive problem-solving. Homework involves keeping a daily record of stressful events to discuss in group.

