**Assessment approach.** Because of the history of human rights violations and misconduct in medical and psychological research, many people of color mistrust research activities (Suite, La Bril, Prim, & Harrison-[name], 2007). This is an important reason to study the feasibility of the proposed data collection strategy and motivation to prioritize brevity of our assessment battery. A record of study participation will be gathered following CONSORT guidelines to quantify enrollment and retention. Assessments will be completed within 1 month prior to the beginning of group and within 1 month after the end of group. The sample will be characterized at the baseline assessment. Participant characteristics including age, gender, race/ethnicity, education, work status and financial and housing stability, will be gathered using a demographic questionnaire. Adherence to group will be quantified based on attendance at sessions and proportion of homework completed (**coded as none/partial/complete as judged by the therapist**).

**Recruitment feasibility.** Aim 1 of this study involves evaluating strategies for recruiting VOC for this type of study. *Enrollment rate*, defined as the number of contacts per enrollment, will be used to optimize the future approach to accrual. There is no target enrollment rate as many can be acceptable; this metric will serve to guide resource allocation. **Gathering information from Veterans and providers about reasons for declining participation or referral, however, will be important in determining the representativeness of the sample.** *Number of enrollments per month* will be viewed as successful if at least four individuals are enrolled per month as that level of recruitment represents a reasonable period (average 2-3 weeks) for a Veteran to wait for a group to begin. *Initiation rate* will be defined as the proportion of Veterans who initiate the intervention among all consented participants. This will inform recruitment strategies (i.e., which strategies lead to the highest proportion of treatment initiation) but also may help to identify areas of improvement in terms of connecting Veterans to the project. As these behaviors are recorded prior to the first session, we do not expect group differences.

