**Acceptability, appropriateness and feasibility.** Relevant to aim 2, participant behavior is one important marker of participants' perceptions of the project and their ability to comply with research procedures. *Retention rate* will be defined as the percent of enrolled sample completing all assessment time points; at least 80% completion will be considered successful. *Per protocol completion rate* will be defined as the proportion of subjects who complete 6 or more sessions among those who initiate treatment; at least 90% completion will be considered successful. *Intent-to-treat completion rate* will be defined as the proportion of subjects who complete 6 or more sessions of intervention among all randomized subjects; at least 80% is the target. *Compliance with homework* will be assessed with a goal of at least 80% moderately or fully complete (refer to **Assessment approach**). In addition, Veterans will be directly queried about their experience using the *Acceptability of Intervention Measure (AIM)*, *Intervention Appropriateness Measure (IAM)*, and *Feasibility of Intervention Measure (FIM)*. The 5-item measures have strong content validity, test-retest reliability and sensitivity to change (Weiner et al., 2017). The psychotherapy version of the *Provider Rating Scales*, which were previously used to assess perceptions of VA mental health providers (Spoont et al., 2017), will be used to assess Veterans' perceptions of the group leader. Between-group differences on these measures would likely reflect the difference in content between the two groups.

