We will assess four outcome measures for enrollment and retention: 1) *enrollment rate* defined as the proportion of consented subjects among all screened and eligible patients; 2) *initiation rate* defined as the proportion of subjects who initiate the intervention among all consented subjects; 3) *per protocol completion rate* defined as the proportion of subjects who complete 5 or 6 sessions of intervention among those who start the intervention; 4) *intent-to-treat completion rate* defined as the proportion of subjects who complete 5 or 6 sessions of intervention among all randomized subjects. The 95% CI (based on normal approximation or exact binomial test when appropriate) will be estimated for all these rates for overall and by each intervention group. The rates for the RBSTE and PCT groups will be compared by Fisher's exact test. Multivariable analysis will be also performed to examine the difference in outcomes between intervention groups using logistic regression.

**Aim 2:** *To understand Veterans' views of the acceptability and appropriateness of treatment content, the feasibility of participation, and perceptions of provider behavior and attitudes.*

The AIM, IAM, FIM and Provider Rating Scales will be estimated by mean, SD and 95% CI. Intervention groups will be compared by Wilcoxon rank sum test. Multivariable analysis will be also performed to examine the difference in outcomes between intervention groups using linear regression.

**Aim 3:** *To optimize the strategy for holistic evaluation of intervention effects.*

As aforementioned, we will include a comprehensive list of cardiometabolic, neuroendocrine, and inflammatory markers that had been shown as reliable markers of AL in the literature to derive an AL index for each participant. We hypothesize that AL index at baseline will be associated with perceived discrimination as well as other psychosocial outcomes and that pre to post-intervention changes of AL index will differ between the two groups. We will perform regression analysis and variable selection using LASSO (Tibshirani 1996) to identify a smaller subset of the AL markers at baseline that show significant associations with psychosocial outcome measures. The effect size for pre and post change in AL markers will be estimated. This will inform future efficacy and effectiveness studies in potential reduction of a list of biomarkers to enhance feasibility, efficiency and reduce participant burden.

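### Therapy groups are randomized as units, but the analysis of ratings, the pooled completion interval and the three detectable effects treat Veterans as independent

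*Combined protocol and SAP*

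**What the plan says.** Research Design and Methods sets the unit of allocation: "Randomization will occur at the group level", once a cohort of 4-10 Veterans has enrolled and completed baseline. The same paragraph lists the drawbacks of this choice and sets them aside: "dependence among group members, lack of blinding of the final 1-2 groups), these can be managed". No method for managing the dependence follows there or later. The plan contains no ICC, design effect, random effect, robust variance or group-level summary.

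Sample size aims for four groups per arm averaging six Veterans, about 48 in total; Participants allows a "potential range 24-60". The detectable effects at 80% power and two-sided 5% are 0.60 (pre-post, n = 24), 0.41 (pre-post, n = 48) and 0.83 (between arms, 24 v 24).

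Under Analyses, Aim 1 names normal or exact binomial intervals, Fisher's test and logistic regression for the rates. Aim 2 names mean, SD and 95% interval for the four rating measures, then "Intervention groups will be compared by Wilcoxon rank sum test", then linear regression.

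**The concern.** Members of one therapy group attend the same sessions, and the Provider Rating Scales ask them about their "perceptions of the group leader". Ratings, and to a lesser degree attendance, can therefore resemble each other within a group. If they do, 24 Veterans in four groups carry less information than 24 independent Veterans. Intervals then come out too narrow, p-values too small, and the effect the design can detect is larger than stated.

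Aim 2 is one of three primary aims, and its results are these intervals and comparisons. Sample size also presents 0.83 as an effect that would point to further study, so that figure will be read when the next trial is planned.

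**Working it through.** **Inputs.** From the documents: four groups per arm, mean size m = 6, 24 per arm, 48 in total, two-sided alpha 0.05, power 80%. Assumed, because the documents give none: ICC from 0 to 0.20.

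**Step 1: reproduce the stated effects.** Solve the noncentral t for 80% power with independent Veterans.
- Pre-post, n = 24: noncentrality d√24, 23 df, gives d = 0.597 (stated 0.60).
- Pre-post, n = 48: noncentrality d√48, 47 df, gives d = 0.413 (stated 0.41).
- Between arms: noncentrality d√(24/2), 46 df, gives d = 0.826 (stated 0.83).

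All three reproduce with no allowance for clustering.

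**Step 2: allow for clustering.** The design effect is 1 + (m − 1) × ICC = 1 + 5 × ICC, and each detectable effect is multiplied by its square root. At ICC 0.10, for example, 0.826 × √1.50 = 1.012. The last column instead analyses group means on 4 + 4 − 2 = 6 df, where the between-arm variance is 2v/4 with v = ICC + (1 − ICC)/6.

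| ICC | Design effect | Effective n per arm | Pre-post, one arm | Pre-post, overall | Between arms, design effect only | Between arms, 6 df |
|---|---|---|---|---|---|---|
| 0 | 1.00 | 24.0 | 0.60 | 0.41 | 0.83 | 0.97 |
| 0.01 | 1.05 | 22.9 | 0.61 | 0.42 | 0.85 | 1.00 |
| 0.05 | 1.25 | 19.2 | 0.67 | 0.46 | 0.92 | 1.09 |
| 0.10 | 1.50 | 16.0 | 0.73 | 0.51 | 1.01 | 1.19 |
| 0.20 | 2.00 | 12.0 | 0.85 | 0.58 | 1.17 | 1.38 |

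The rise from 0.83 to 0.97 at ICC 0 is the cost of having only 6 df in that analysis. It is not an error in the plan.

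**Step 3: behaviour of the named methods.** Simulation with eight equal groups of six and no true arm difference. Ratings are normal with a random group effect; completion is beta-binomial.

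| Quantity | ICC 0.01 | 0.05 | 0.10 | 0.20 |
|---|---|---|---|---|
| Wilcoxon, type I error at nominal 5% | 5.5% | 7.6% | 10.5% | 16% |
| Pooled 95% interval for a mean rating, coverage | 94% | 92% | 89% | 83% |
| Pooled exact completion interval, 80% rate, coverage | 95% | 93% | 90% | 84% |
| Pooled exact completion interval, 90% rate, coverage | 97% | 96% | 94% | 89% |
| Per-arm exact completion interval, 80% rate, coverage | 98% | 97% | 95% | 91% |
| Fisher, 80% rate, type I error | 3.0% | 4.5% | 6.9% | 11.8% |
| Fisher, 90% rate, type I error | 2.0% | 3.2% | 4.7% | 8.6% |

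A t-test on group means holds 4.8-5.1% for ratings throughout. With unequal groups (4, 5, 5, 10 v 4, 4, 6, 10) the Wilcoxon figures are 5.4, 8.2, 11.6 and 18.2%. With six groups of four (n = 24, the bottom of the planned range) they are 4.8, 6.1, 7.9 and 11.2%.

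**Step 4: what is not touched.** Enrollment and initiation are settled before any session; on initiation, Recruitment feasibility says "As these behaviors are recorded prior to the first session, we do not expect group differences". The success thresholds, such as "at least 90% completion will be considered successful", are applied to point estimates, so interval width does not enter them. For change scores no between-arm test is named, so there the issue lies in the Sample size figures and in any ordinary regression used.

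**The case against.** The strongest reply is that this is a pilot. Sample size says it was not sized for hypothesis testing. Analyses cautions about effect sizes from pilots, puts the primary analysis overall and within arm, and compares arms only where needed. With no ICC given, all harm is conditional, and near 0.01 it is small. This limits the weight of the point but does not remove it. Aims 1 and 2 state their comparisons without that condition, and the overall interval for a mean rating loses coverage whether or not arms are compared.

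A reader might infer that the Fisher comparison of completion is also unsound. The figures do not support that at modest ICC. Fisher stays below 5% through ICC 0.05, and through 0.10 at a 90% rate. A t-test on group completion proportions would itself reject about 5.4-6.3% at ICC 0.01-0.05, so replacing Fisher would not help there.

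A reader might also infer that 0.83 is miscalculated and should read 0.97. It is correct for independent Veterans; what is missing is the statement of that assumption.

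Finally, four groups per arm give few degrees of freedom. That is true. It is a reason to report the wider uncertainty, not to leave it out.

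**Conclusion.** The point holds in limited form. The omission is certain: dependence is conceded, called manageable, and given no method. It affects the Wilcoxon test, linear regression and intervals for the ratings, the pooled completion interval, and the reading of 0.60, 0.41 and 0.83.

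The size depends on an ICC that the documents do not supply. Harm is slight near 0.01. From about 0.05 it is material for the ratings and, at an 80% rate, begins to show in the pooled completion interval. Fisher's test and the per-arm exact completion interval become a concern only at about 0.10 or above. The figures assume eight groups of six unless stated.

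It would be tempting to conclude that the feasibility verdict fails. The documents do not support that: the success criteria are point-estimate thresholds, and the enrollment and initiation analyses stand as planned. What suffers is interpretation of Aim 2 and planning of the next trial. It should be fixed.

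**What to change.** 1. **Ratings, and change scores if compared.** Compare arms at group level, by a t-test on group means weighted by size or a mixed model with a random group intercept. Use df equal to groups formed minus 2 (6 if eight form). If very few groups form, report estimates only.
2. **Intervals for mean ratings.** Build the pooled interval from group means, using their pooled within-arm variance on groups minus 2 df. On groups minus 1 df, a true arm difference would count as noise and coverage would rise to about 97-99%. Per arm, use the wider group-mean interval, or keep the planned one and state that it ignores clustering.
3. **Completion.** Keep Fisher's test and the per-arm exact interval, stating that they ignore clustering; read the logistic regression with the same caution. For the pooled rate add an exact interval on n/(1 + (m − 1) × ICC), with m the sum of squared group sizes divided by n. For the unequal sizes above, m = 334/48 = 6.96. Truncate the ICC at zero, and set it to zero if everyone completes. Note that coverage can fall to about 92% with unequal groups at ICC 0.20.
4. **ICC.** Report the observed value with its interval, labelled imprecise.
5. **Sample size.** State that 0.60, 0.41 and 0.83 assume no clustering. Add that for ICC 0-0.20 the design effect alone gives 0.60-0.85, 0.41-0.58 and 0.83-1.17, and that a between-arm analysis on 6 df gives 0.97-1.38.

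**Limit.** Interventions says "Therapists in both conditions will be VA mental health providers" but not how many groups each leads. If a therapist leads several, group-level methods do not remove dependence at therapist level, and the plan should say so.

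**Cost.** Wording only; no extra Veterans or data. Stated effects become less favourable and intervals wider. For ICC 0.01-0.20 the per-arm group-mean interval is about 1.5-2.1 times the planned width. Pooled, the ratio is 1.17-1.63 on 7 df with equal arms. Scaling by the t quantiles, 2.447/2.365 = 1.03, gives roughly 1.2-1.7 on 6 df. The size-weighted t-test rejects 5.1-5.9%, and the mixed model on 6 df is conservative at 1.5-4.0%. The ICC will be poorly estimated: at a true 0.05, median 95% limits are −0.10 and 0.45.

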**Allostatic load** will be assessed pre and post intervention by measuring 10 markers of interest, specifically hemoglobin (Hb) A1c, systolic and diastolic blood pressure (SBP, DBP), high density lipoprotein (HDL), triglycerides, urine epinephrine (Epi) and norepinephrine (NE), waking salivary cortisol, interleukin (IL)-6, and hsCRP. **Venous blood will be drawn via vena puncture between 8-10 AM after overnight fasting and sent to the VA clinical chemistry lab to measure Hb A1c and the lipid panel (for HDL and triglycerides). Plasma from 5mL of blood will be collected and frozen at -80 C until assayed to measure IL-6 and hsCRP using electrochemiluminescence assay (Mesoscale Discovery). Spot urine will be collected for Epi and NE and frozen at -80 C until assayed using ELISA-based immunoassay and adjusted for creatinine levels, which are well representative of general sympathetic output of an individual. Salivary cortisol levels will be measured in saliva collected the morning of the blood draw visit upon wakening. Saliva samples will be frozen at -80 C until assayed using immunoassay (Salimetrics). Both pre and post samples from a given participant will be assayed together using reagents from a single lot number by one technician who is blinded to the condition. All biomarker assays will be done in [name] lab where they are routinely performed, and the intra- and inter-assay CV's of these proposed markers are <10%. Seated SBP and DBP will be measured after a 5-min of rest, and the average from 3 readings will be used. The AL index for each participant will be calculated by assigning 1 to the highest quartile values vs. the rest 0 for each marker and summing them (Rosemberg, Granner, Li & Seng, 2020).** Thus, a possible range of 0 to 10 would emerge, indicating the lowest to highest AL across the participants. We acknowledge that there have been differing ways for AL index calculation as well as included markers. Our proposed methods and the markers are based on the best consensus from a number of studies and reviews that also demonstrated evidence of AL reflecting chronic stress and eventual health outcomes including all-cause mortality (Duong et al., 2017; Guidi, Lucente, Sonino, & Fava, 2021; Juster, McEwen & Lupien, 2010).

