**Sample size.** As a feasibility study, the decision about sample size is not about establishing sufficient power to detect change in clinical outcomes but rather about demonstrating the viability of a future larger-scale study. The sample size was determined based on practical and quantitative considerations. We will aim for enrollment of 4 groups of each type of intervention, each with approximately 6 Veterans (average 6, range 4-10), leading to a total sample size of approximately 48 (24/cell) in the 15-month recruitment period. This rate of enrollment would demonstrate feasibility of a larger future study in that we would demonstrate that a steady flow of adequately sized intervention groups can be recruited. Given that this is a pilot and feasibility study, we are looking for clinical signal and feasibility rather than examining efficacy. All sample size analyses were performed using statistical package R. A two-sided type I error of 0.05 was assumed.

The sample size assessment was conducted for assessing the enrollment and completion rates. First, we assessed the precision of estimates based on projected sample size. We considered a range of target rate from 0.60 to 0.90 and estimated the width of the 95% exact binomial confidence interval for enrollment and completion rates for overall and for each intervention group (see **Table 1**).

**Table 1.** The width of 95% confidence intervals for enrollment and completion rates

Sample size	Estimated rate						
	0.60	0.65	0.70	0.75	0.80	0.85	0.90
48	0.267	0.261	0.251	0.239	0.222	0.201	0.174
24	0.365	0.357	0.345	0.329	0.308	0.282	0.249

From **Table 1**, if an estimated intervention initiation rate is 0.80, a sample size of 48 (total) and 24 (per intervention group) will produce a two-sided 95% confidence interval with a width of 0.222 and 0.308,

respectively. If an estimated intervention initiation rate is 0.90, the width of the 95% CI is reduced (becomes more precise, see **Table 1**) with the same sample size projected above.

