As a feasibility study, the sample size was not projected to ensure enough study power for hypothesis testing. We assessed the effect size of the outcome (such as Brief PHI, DASS-21, TSDS) that can be detected with the planned sample size and 80% power. The effect size for change in outcome from baseline to post treatment in each intervention group and overall was estimated based on a paired t-test. With a sample size of 24 per group and 48 in total, we could detect an effect size of 0.60 and 0.41, which are moderate effect sizes. To compare the outcome change between the RBSTE and PCT groups, with 24 per group, we could detect a moderate effect size of 0.83 for the difference with 24 subjects per group. This effect size would be clinically meaningful thus signaling the need for additional study.

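### Aim 3 relates baseline allostatic-load markers to psychosocial scores, and shortens the marker list by LASSO, without fixing age and gender in the models

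*Combined protocol and SAP*

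**What the plan says.** All references are to the combined protocol and SAP, Research Design and Methods.

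- **Analyses, Aim 3.** The baseline AL index is hypothesised to be associated with perceived discrimination and other psychosocial outcomes. Regression and LASSO are then used "to identify a smaller subset of the AL markers at baseline that show significant associations with psychosocial outcome measures". The stated use is a possible shortening of the biomarker list in later efficacy and effectiveness studies. The AL markers are the only predictors described.
- **Allostatic load.** The index is "calculated by assigning 1 to the highest quartile values vs. the rest 0 for each marker and summing them". No age- or sex-specific cut-offs are stated.
- **Participants.** Entry criteria begin "1) self-identified as a BIPOC, (2) Veteran, (3) age 18 or older". There is no upper age limit and no restriction by gender.
- **Assessment approach.** "Participant characteristics including age, gender, race/ethnicity, education, work status and financial and housing stability, will be gathered using a demographic questionnaire". Both variables are therefore available at baseline.
- **Analyses, opening paragraph.** Variables become candidates for the multivariable model if they are associated with the outcome, or differ between arms, at p<0.15. Backward elimination keeps those with p<0.10. Aims 1 and 2 each say that multivariable analysis will be performed. Aim 3 does not, and nothing extends the rule to the LASSO.

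**The concern.** Many cardiometabolic and inflammatory markers plausibly change with age, and some differ by sex. This is general physiology and is not stated in the documents. With cut-offs taken over the whole sample, older Veterans could collect AL points because of age. If psychosocial scores also vary with age, an unadjusted marker-score association carries an age component.

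The direction matters. If distress falls with age while markers rise, the age component runs against the hypothesised positive link and can hide a real association. It can also make a marker look informative when it only stands in for age. A marker wrongly dropped from the shortlist might not be measured in the next trial, which then could not correct the error.

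The general covariate rule is weak protection here. It keeps age only when age passes a p-value threshold in a sample of about 48. Its other trigger, a difference between arms, has no bearing on a pooled baseline association.

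**Working it through.** **Inputs from the plan (Sample size).** The total is "leading to a total sample size of approximately 48 (24/cell) in the 15-month recruitment period". "A two-sided type I error of 0.05 was assumed". Detectable effects are those "that can be detected with the planned sample size and 80% power".

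**The plan's own figures.** "With a sample size of 24 per group and 48 in total, we could detect an effect size of 0.60 and 0.41", and 0.83 is given for the between-group comparison. Noncentral-t power solved at 80% gives 0.597 (paired, n=24), 0.413 (paired, n=48) and 0.826 (24 per group), so all three reproduce. The plan gives no figure for the Aim 3 association or the LASSO.

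**Assumed inputs, not in the documents.** Age-marker correlation a = 0.3 to 0.5; age-score correlation b = -0.2 to -0.4; true age-adjusted correlation ρ = 0 or 0.35; n = 48.

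**Step 1: what the unadjusted analysis estimates.** The marginal correlation is r = ab + ρ√[(1-a²)(1-b²)].

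- ρ = 0: r = 0.3×(-0.2) = -0.06; 0.4×(-0.3) = -0.12; 0.5×(-0.4) = -0.20.
- ρ = 0.35: r = -0.06 + 0.35×0.935 = 0.27; -0.12 + 0.35×0.874 = 0.19; -0.20 + 0.35×0.794 = 0.08.

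**Step 2: rejection rates.** By Fisher's z, with m = atanh(|r|)×√45, the rejection probability is Φ(m-1.96) + Φ(-m-1.96). For r = -0.20, m = 0.2027×6.708 = 1.36, which gives 0.275. The same formula gives 0.069 for r = -0.06 and 0.128 for r = -0.12. Simulation (20,000 samples per setting) agrees, and also covers the general rule (p<0.15 entry, p<0.10 retention, age as the only candidate) and age fixed in the model:

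| a, b | False positives: none / rule / fixed | Power at ρ=0.35: none / rule / fixed |
|---|---|---|
| 0.3, -0.2 | 7% / 7% / 5% | 0.45 / 0.61 / 0.69 |
| 0.4, -0.3 | 13% / 8% / 5% | 0.25 / 0.62 / 0.69 |
| 0.5, -0.4 | 28% / 10% / 5% | 0.08 / 0.66 / 0.69 |

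The rule helps least when the age-marker link is strong and the age-score link weak. At (0.5, -0.2), r = -0.10 + 0.35×0.849 = 0.20, unadjusted power is about 0.27, the rule gives 0.53, and fixing age gives about 0.69.

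**Step 3: how often a p<0.10 threshold passes age.** With m = atanh(|b|)×√45, the probability is approximately Φ(m-1.645): 0.39 at |b| = 0.2, 0.67 at 0.3 and 0.88 at 0.4. Age is therefore dropped in about 61%, 33% and 12% of samples.

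**Step 4: the LASSO itself.** A five-fold cross-validated LASSO was simulated with n = 48 and ten markers, five of them age-related and none directly linked to the score (300 runs per setting). The table shows how often an age-related marker is selected. Both correlations were taken as positive here.

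| Age-marker, age-score | Age omitted | p<0.10 screen | Age forced in |
|---|---|---|---|
| 0.3, 0.3 | 0.15 | 0.11 | 0.11 |
| 0.4, 0.3 | 0.16 | 0.10 | 0.09 |
| 0.4, 0.4 | 0.25 | 0.08 | 0.08 |
| 0.5, 0.4 | 0.30 | 0.08 | 0.08 |

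With no age links, selection is about 0.10 with age omitted and 0.09 with age forced in. Forcing age in therefore brings selection back to about that level.

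**The case against.** The strongest reply is that the general covariate rule stands above all three aims, and Aim 3 plans regression, so the rule can be read as covering at least the AL-index regression. If it does, most of the loss disappears: the worst power rises from 0.08 to 0.66, and LASSO selection under a p<0.10 screen is close to that with age forced in. This stands. A reader might infer from the unadjusted figures that Aim 3 is left with power as low as 0.08. The documents do not support that for any regression the rule covers. What remains is that the rule never guarantees age, falls short of fixing it in the single-marker simulations, and is not stated to reach the LASSO.

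The second reply is that the premises are external. No section says that the markers depend on age or sex, or that distress falls with age. This also stands. The bias needs both links, and the power loss needs the age component to oppose the true association. A reader might take gender to be shown as an equal problem. It was not simulated, and it is included because the same reasoning applies.

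The third reply is that the analyses are declared to be for feasibility and hypothesis generation, and that the LASSO only informs a possible shortening of the list. This limits the weight of the point but does not remove it, because the shortlist is a stated product of one of the three primary aims.

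**Conclusion.** The point holds as a modest improvement to an exploratory deliverable. Aim 3 fixes neither age nor gender, and the only covariate rule is data-driven and of unclear reach. Whether the loss is large depends on a question the plan leaves open. If the rule does not apply, the assumed correlations give false-positive rates up to 28% and power down to 0.08. If it does apply, the figures are about 10% and 0.53 at worst in the settings examined, against about 5% and 0.69 with age fixed.

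These figures rest on n = 48, linear relations, age as the only confounder and correlations that the documents do not supply. With no age-score relation there is no false-positive inflation. A reader might infer that the shortlist is bound to reflect age, or that the pilot's conclusions are at risk. The documents support neither: the bias is conditional, and the recruitment, retention and acceptability results do not depend on this analysis.

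**What to change.** Add to the Aim 3 analysis text that:

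- age and gender stay in every baseline AL-psychosocial regression whatever their p-values, and are exempt from backward elimination;
- both enter the LASSO as unpenalised terms;
- the marker shortlist is taken from the adjusted model, with the unadjusted result shown beside it.

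The cost is a sentence or two of text and about two degrees of freedom of 48 (one for age as a linear term, one for gender in two categories). Both variables are already collected, so there is no new data, participant burden or design change.
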